Appendix 6:Immune-Modified Response Evaluation Criteria in Solid Tumors (imRECIST)

TUMOR MEASURABILITY

At baseline, tumor lesions/lymph nodes will be categorized as measurable or non-measurable as described below. All measurable and non-measurable lesions should be assessed at screening and at subsequent protocol-specified tumor assessment timepoints. Additional assessments may be performed as clinically indicated for suspicion of progression.

DEFINITION OF MEASURABLE LESIONS

Tumor Lesions

Tumor lesions must be accurately measured in at least one dimension (longest diameter in the plane of measurement is to be recorded) with a minimum size as follows:

- 10 mm by computed tomography (CT) or magnetic resonance imaging (MRI) scan (CT/MRI scan slice thickness/interval \leq 5 mm)
- 10-mm caliper measurement by clinical examination (lesions that cannot be accurately measured with calipers should be recorded as non-measurable)
- 20 mm by chest X-ray

Malignant Lymph Nodes

To be considered pathologically enlarged and measurable, a lymph node must be \geq 15 mm in the short axis when assessed by CT scan (CT scan slice thickness recommended to be \leq 5 mm). At baseline and follow-up, only the short axis will be measured and followed. Additional information on lymph node measurement is provided below (see "Identification of Target and Non-Target Lesions," "New Lesions," and "Calculation of Sum of Diameters").

DEFINITION OF NON-MEASURABLE LESIONS

Non-measurable tumor lesions encompass small lesions (longest diameter $<$ 10 mm or pathological lymph nodes with short axis \geq 10 mm but $<$ 15 mm) as well as truly non-measurable lesions. Lesions considered truly non-measurable include leptomeningeal disease, ascites, pleural or pericardial effusion, inflammatory breast disease, lymphangitic involvement of skin or lung, peritoneal spread, and abdominal mass/abdominal organomegaly identified by physical examination that is not measurable by reproducible imaging techniques.

SPECIAL CONSIDERATIONS REGARDING LESION MEASURABILITY

Bone lesions, cystic lesions, and lesions previously treated with local therapy require particular comment, as outlined below.

Bone Lesions:

- Technetium-99m bone scans, sodium fluoride positron emission tomography scans, and plain films are not considered adequate imaging techniques for measuring bone

Appendix 6:Immune-Modified Response Evaluation Criteria in Solid Tumors (imRECIST)

lesions. However, these techniques can be used to confirm the presence or disappearance of bone lesions.

- Lytic bone lesions or mixed lytic-blastic lesions with identifiable soft tissue components that can be evaluated by cross-sectional imaging techniques such as CT or MRI can be considered measurable lesions if the soft tissue component meets the definition of measurability described above.
- Blastic bone lesions are non-measurable.

Cystic Lesions:

- Lesions that meet the criteria for radiographically defined simple cysts should not be considered malignant lesions (neither measurable nor non-measurable) since they are, by definition, simple cysts.
- Cystic lesions thought to represent cystic metastases can be considered measurable lesions if they meet the definition of measurability described above. However, if non-cystic lesions are present in the same patient, these are preferred for selection as target lesions.

METHODS FOR ASSESSING LESIONS

All measurements should be recorded in metric notation, using calipers if clinically assessed. All baseline evaluations should be performed as close as possible to the treatment start and never more than 4 weeks before the beginning of the treatment.

The same method of assessment and the same technique should be used to characterize each identified and reported lesion at baseline and during the study. Imaging-based evaluation should always be the preferred option.

CLINICAL LESIONS

Clinical lesions will only be considered measurable when they are superficial and ≥ 10 mm in diameter as assessed using calipers (e.g., skin nodules). For the case of skin lesions, documentation by color photography, including a ruler to estimate the size of the lesion, is suggested.

CHEST X-RAY

Chest CT is preferred over chest X-ray, particularly when progression is an important endpoint, since CT is more sensitive than X-ray, particularly in identifying new lesions. However, lesions on chest X-ray may be considered measurable if they are clearly defined and surrounded by aerated lung.

CT AND MRI SCANS

CT is the best currently available and reproducible method to measure lesions selected for response assessment. In this guideline, the definition of measurability of lesions on CT scan is based on the assumption that CT slice thickness is ≤ 5 mm. When CT scans

Appendix 6:Immune-Modified Response Evaluation Criteria in Solid Tumors (imRECIST)

have slice thickness of > 5 mm, the minimum size for a measurable lesion should be twice the slice thickness. MRI is also acceptable.

If prior to enrollment it is known that a patient is unable to undergo CT scans with IV contrast because of allergy or renal insufficiency, the decision as to whether a non-contrast CT or MRI (without IV contrast) will be used to evaluate the patient at baseline and during the study should be guided by the tumor type under investigation and the anatomic location of the disease. For patients who develop contraindications to contrast after baseline contrast CT is done, the decision as to whether non-contrast CT or MRI (enhanced or non-enhanced) will be performed should also be based on the tumor type and the anatomic location of the disease, and should be optimized to allow for comparison with prior studies, if possible. Each case should be discussed with the radiologist to determine if substitution of these other approaches is possible and, if not, the patient should be considered not evaluable from that point forward. Care must be taken in measurement of target lesions and interpretation of non-target disease or new lesions on a different modality, since the same lesion may appear to have a different size using a new modality.

ENDOSCOPY, LAPAROSCOPY, ULTRASOUND, TUMOR MARKERS, CYTOLOGY, HISTOLOGY

Endoscopy, laparoscopy, ultrasound, tumor markers, cytology, and histology cannot be used for objective tumor evaluation.

ASSESSMENT OF TUMOR BURDEN

To assess objective response or future progression, it is necessary to estimate the overall tumor burden at baseline and use this as a comparator for subsequent measurements.

IDENTIFICATION OF TARGET AND NON-TARGET LESIONS

When more than one measurable lesion is present at baseline, all lesions up to a maximum of five lesions total (and a maximum of two lesions per organ) representative of all involved organs should be identified as target lesions and will be recorded and measured at baseline. This means that, for instances in which patients have only one or two organ sites involved, a maximum of two lesions (one site) and four lesions (two sites), respectively, will be recorded. Other lesions (albeit measurable) in those organs will be considered non-target lesions.

Target lesions should be selected on the basis of their size (lesions with the longest diameter) and be representative of all involved organs, but in addition should lend themselves to reproducible repeated measurements. It may be the case that, on occasion, the largest lesion does not lend itself to reproducible measurement, in which circumstance the next largest lesion that can be measured reproducibly should be selected.

Appendix 6:Immune-Modified Response Evaluation Criteria in Solid Tumors (imRECIST)

Lymph nodes merit special mention since they are normal anatomical structures that may be visible by imaging even if not involved by tumor. As noted above, pathological nodes that are defined as measurable and may be identified as target lesions must meet the criterion of a short axis of ≥ 15 mm by CT scan. Only the short axis of these nodes will contribute to the baseline sum. The short axis of the node is the diameter normally used by radiologists to judge if a node is involved by solid tumor. Lymph node size is normally reported as two dimensions in the plane in which the image is obtained (for CT, this is almost always the axial plane; for MRI, the plane of acquisition may be axial, sagittal, or coronal). The smaller of these measures is the short axis. For example, an abdominal node that is reported as being $20\text{ mm} \times 30\text{ mm}$ has a short axis of 20 mm and qualifies as a malignant, measurable node. In this example, 20 mm should be recorded as the node measurement. All other pathological nodes (those with short axis ≥ 10 mm but < 15 mm) should be considered non-target lesions. Nodes that have a short axis of < 10 mm are considered non-pathological and should not be recorded or followed.

All lesions (or sites of disease) not selected as target lesions (measurable or non-measurable), including pathological lymph nodes, should be identified as non-target lesions and should also be recorded at baseline. Measurements are not required. It is possible to record multiple non-target lesions involving the same organ as a single item on the Case Report Form (CRF) (e.g., "multiple enlarged pelvic lymph nodes" or "multiple liver metastases").

NEW LESIONS

New lesions identified after baseline will be evaluated for measurability with use of the same criteria applied to prospective target lesions at baseline per RECIST (e.g., non-lymph node lesions must be ≥ 10 mm on the longest diameter; new lymph nodes must be ≥ 15 mm on the short axis [see note below]). All new lesions (measurable or non-measurable) must be assessed and recorded at the time of identification and at all subsequent tumor assessment timepoints.

Up to a maximum of five measurable new lesions total (and a maximum of two lesions per organ) can be included in the calculation of tumor burden that is performed as part of the tumor response evaluation. New lesion types that would not qualify as target lesions per RECIST cannot be included in the calculation of tumor burden and thus will not affect overall tumor response evaluation. New lesions that are not measurable at first appearance but meet measurability criteria at a subsequent timepoint can be included in the tumor response evaluation from that point on, if the maximum number of measurable new lesions has not been reached.

Note regarding new lymph node lesions: If at first appearance the short axis of a lymph node lesion is ≥ 15 mm, it will be considered a measurable new lesion. If at first appearance the short axis of a lymph node lesion is ≥ 10 mm and < 15 mm, the lymph node will not be considered measurable but will still be considered a new lesion and

Cobimetinib, atezolizumab, vemurafenib — F. Hoffmann-La Roche Ltd

165 / Protocol MO39136, Version 5.0

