6.4.3 Exploratory Efficacy Endpoints

The exploratory efficacy endpoints are listed in [Table 1](#) and are as follows:

- Intracranial ORR defined as the proportion of patients with either a CR or PR in their intracranial disease as assessed by the investigator according to iRANO criteria based on two consecutive assessments ≥ 4 weeks apart.
- Objective response rate in intracranial, extracranial and overall disease as determined by investigator according to immune-modified RECIST with modified measurability definition for intracranial lesions (≥ 0.5 cm by MRI) and allowing up to five intracranial target lesions.
- Intracranial, extracranial and overall PFS is determined by the investigator according to immune-modified RECIST.

- Intracranial, extracranial and overall DOR is determined by the investigator according to immune-modified RECIST
Objective response, PFS and DOR, as determined by the investigator according to immune modified RECIST, will be analysed using the same methods as described in Section 6.4.2.
- Radiotherapy-assisted PFS defined as time from study treatment initiation to the first occurrence of disease progression or death from any cause, whichever occurs first, as determined by the investigator according to RECIST v1.1 modified by excluding ≤ 3 lesions that can be treated by SRT from the sum of largest diameters from baseline onwards
- Timing of increase or change in corticosteroid use during treatment will be based on corticosteroid used for symptomatic control as indicated in the eCRF
- Time from study treatment initiation to subsequent intracranial and systemic anti-cancer treatment
- Change from baseline scores over time in treatment/disease-related symptoms as evaluated by the EORTC QLQ-C30 and QLQ-BN20 questionnaires will be summarized descriptively including the mean change from baseline of linear-transformed scores for all subscales of the EORTC QLQ-C30 and QLQ-BN20 according to the EORTC scoring manual guideline at each assessment time point for each cohort, including progression, treatment discontinuation and post-study discontinuation. The mean (and 95% CI) and median of the absolute scores and the change from baseline will be reported for interval and continuous variables. Only patients with a non-missing baseline assessment and at least one non-missing post-baseline assessment will be included in PRO analyses.

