### **5.5.1.2 Intracranial, Extracranial and Overall Objective Response Rate – Immune-Modified RECIST**

ORR in intracranial, extracranial and overall disease are defined as described in Sections [5.4.2.1](#), [5.4.2.2](#), and [5.4.2.3](#) but determined by investigator according to immune-modified RECIST with modified measurability definition for intracranial lesions ( $\geq 0.5$  cm by MRI) and allowing up to five intracranial target lesions.

Intracranial, extracranial, and overall ORR will be analyzed using the same methods as described in Section [5.3.2](#).

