### **5.5.1.4 Intracranial, Extracranial, and Overall Duration of Response – Immune-Modified RECIST**

Intracranial, extracranial, and overall DOR are defined as described in Section [5.4.2.5](#) but determined by the investigator according to immune-modified RECIST.

Intracranial, extracranial, and overall DOR will be analyzed using the same methods as described in Section [5.4.2.5](#).

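### The imRECIST appendix was not adapted to the trial's intracranial rule: new brain lesions face a tighter cap, and possibly a higher size threshold, than baseline brain targets

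*Protocol*

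**What the plan says.** Protocol 6.4.3 defines the exploratory response rate by "immune-modified RECIST with modified measurability definition for intracranial lesions (≥ 0.5 cm by MRI) and allowing up to five intracranial target lesions". SAP 5.5.1.2 uses the same definition. Neither says how new brain lesions are to be counted.

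Protocol 4.5.6 refers to Appendix 6 for the imRECIST rules. On new lesions, Appendix 6 says:

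- Measurability is judged "with use of the same criteria applied to prospective target lesions at baseline per RECIST", followed by an example: "non-lymph node lesions must be ≥ 10 mm on the longest diameter".
- "Up to a maximum of five measurable new lesions total (and a maximum of two lesions per organ) can be included" in the tumour burden.
- Non-measurable new lesions, and measurable ones beyond the cap, count only in deciding whether CR has been reached. They are recorded as present or absent, without measurement, and play no part in PD. The response table gives PR whenever targets plus counted new lesions meet PR, whatever the other lesions do.

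For PFS and DOR, SAP 5.5.1.3 and 5.5.1.4 refer back to the RECIST definitions, "but determined by the investigator according to immune-modified RECIST". The intracranial modification is not repeated there.

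**The concern.** imRECIST does not call PD on a new lesion. It adds the lesion to the sum of diameters and lets the sum decide. That works only if old and new lesions enter the sum on comparable terms. Here the baseline part of the intracranial sum can hold five lesions from 5 mm. The new part can hold two brain lesions, and on the literal wording only from 10 mm. A 6 mm brain metastasis present at baseline can be a target; the same lesion appearing later may count for nothing.

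The exploratory imRECIST response rate, PFS and DOR, intracranial and overall, could then look better than consistent counting would show, and results could depend on which text a site follows. Later repair would be difficult, because diameters of new brain lesions judged non-measurable need not be recorded.

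**Working it through.** No sample size, power or confidence interval in the plan depends on these rules, so there is no stated figure to reproduce. The check applies the Appendix 6 rules to assumed patients. All lesion sizes are illustrative assumptions.

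**Rules (Appendix 6)**

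- Burden = sum of target diameters + diameters of counted new lesions.
- PR: burden at least 30% below the baseline sum.
- PD: burden at least 20% and at least 5 mm above the smallest sum on study.
- Otherwise SD. Response needs a second assessment at least 4 weeks later.

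**Counting rules for new brain lesions**

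- A, literal Appendix 6: from 10 mm, at most two.
- B, 0.5 cm carried over but cap unchanged: from 5 mm, at most two.
- C, as for baseline brain targets: from 5 mm, at most five.

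**Patient 1.** Baseline 60 mm; 35 mm at one scan (PR); next scan 35 mm plus six new 6 mm lesions. Smallest sum is 35 mm.

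- A: 35 mm; 35/60 - 1 = -42%; PR confirmed.
- B: 35 + 2×6 = 47 mm; 47/35 - 1 = +34%, +12 mm; PD.
- C: 35 + 5×6 = 65 mm; 65/35 - 1 = +86%, +30 mm; PD.

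In patients 2 to 5 the new lesions are first seen at the scan that shows the target shrinkage, so the smallest earlier sum is baseline. A PR is confirmed if the picture is the same at least 4 weeks later.

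| Patient | Target sum (mm) | New brain lesions | A | B | C |
|---|---|---|---|---|---|
| 2 | 50 to 30 | four of 8 mm | 30, -40%, PR | 30+16=46, -8%, SD | 30+32=62, +24% (+12 mm), PD |
| 3 | 50 to 20 | five of 6 mm | 20, -60%, PR | 20+12=32, -36%, PR | 20+30=50, 0%, SD |
| 4 | 100 to 40 | five of 12 mm | 40+24=64, -36%, PR | 64, -36%, PR | 40+60=100, 0%, SD |
| 5 | 100 to 20 | three of 6 mm | 20, -80%, PR | 20+12=32, -68%, PR | 20+18=38, -62%, PR |

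**Reading the results**

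- Patients 1 and 2 change category mainly through the size threshold. Under B, with the cap still at two, neither keeps PR.
- Patients 3 and 4 show the cap acting alone (B against C). In patient 4 every new lesion exceeds 10 mm, so the result does not depend on how the size wording is read.
- Patient 5 is PR under all three rules. Aligning the rules reduces such responses but does not remove them.
- The cap effect depends on timing. If patient 3 had already reached 20 mm at an earlier scan, B gives 32/20 - 1 = +60%, +12 mm, which is PD despite the cap.

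**The case against.** Several points on the other side have force.

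*The 10 mm figure is only an example.* A reader might infer that Appendix 6 fixes 10 mm for new brain lesions. It does not clearly do so. The governing phrase ties new lesions to the criteria for baseline targets, and the endpoint modifies measurability for intracranial lesions in general. Read together, 0.5 cm may already apply, at least to the response rate. Appendix 6 also gives 10 mm and two per organ for baseline targets, and there the endpoint text plainly takes precedence. So the threshold is unsettled rather than wrong. The cap on new lesions is not an example, and the endpoint text raises only the number of target lesions.

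*ORR and DOR need not differ.* A reader might infer from SAP 5.5.1.2 to 5.5.1.4 that response and its duration follow different rules. The documents show only unrepeated wording. The RECIST PFS and DOR sections (SAP 5.4.2.4 and 5.4.2.5) do not repeat the modification either, although SAP 1.2 sets it for RECIST disease status generally.

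*imRECIST tolerates new lesions by design.* True, but it does so by adding them to the burden. A new lesion that later becomes measurable can also be counted from then on if the cap is not full. Neither fact explains counting new brain lesions differently from baseline ones.

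*The effect may be rare.* A reader might infer that small new brain metastases are the usual form of intracranial failure, so that imRECIST results are materially inflated. The documents do not say this. Protocol 3.3.5 says only that intracranial progression with controlled extracranial disease has become more common. It gives nothing on new against existing lesions, or on their size.

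**Conclusion.** The point holds for the exploratory, investigator-assessed imRECIST endpoints. Appendix 6 was not adapted to the intracranial rule. The cap of two new lesions per organ is clear and at odds with five baseline brain targets; the size threshold for new brain lesions is left open. In assumed patients the mismatch turns SD into PR through the cap alone (32 mm, -36%, against 50 mm, 0%) and PD into PR on the literal wording (35 mm, -42%, against 65 mm, +86% from nadir). Other patterns do not change category. The documents give no frequency, so no effect on the reported rates can be estimated.

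The mismatch does not reach the primary endpoint, which is IRC-assessed under RECIST v1.1, or the RECIST v1.1 secondary endpoints; there an unequivocal new malignant lesion is PD. Treatment decisions also follow RECIST v1.1. The study is descriptive, and these results will stand beside the imRECIST ones. Priority is low.

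**What to change.** In Protocol Appendix 6, state that new intracranial lesions are measurable from 0.5 cm by MRI and that up to five enter the tumour burden. Count them separately from the allowance for new extracranial lesions. Under the present limit of five in total, five new brain lesions would use up the allowance and drop new extracranial lesions from overall imRECIST. Repeat the modified definition in SAP 5.5.1.3 and 5.5.1.4 so that imRECIST ORR, PFS and DOR use one rule.

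The cost is wording in one appendix and two SAP sections. New brain lesions of 5 to 9 mm would have to be measured, and scans already read under the 10 mm wording may need re-reading. Exploratory imRECIST results would become slightly less favourable.

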Appendix 6:Immune-Modified Response Evaluation Criteria in Solid Tumors (imRECIST)

should be identified as a non-measurable new lesion. If at first appearance the short axis of a lymph node is < 10 mm, the lymph node should not be considered pathological and should not be considered a new lesion. A lymph node can subsequently become measurable, when the short axis is ≥ 15 mm.

CALCULATION OF SUM OF DIAMETERS

A sum of the diameters (longest diameter for non-lymph node lesions, short axis for lymph node lesions) will be calculated for all target lesions at baseline as a measure of tumor burden. At each subsequent tumor assessment, a sum of the diameters (longest diameter for non-lymph node lesions, short axis for lymph node lesions) will be calculated for all target lesions plus measurable new lesions (up to five new lesions, with a maximum of two new lesions per organ) that have emerged after baseline. Hence, each net percentage change in tumor burden per assessment accounts for the size and growth kinetics of both old lesions and new lesions as they appear.

Measuring Lymph Nodes

If at first appearance the short axis of a new lymph node lesion is ≥ 15 mm, it will be considered a measurable new lesion and may be included in the sum of the diameters. If the new lymph node lesion is included in the sum of diameters, it will continue to be measured and included in the sum of diameters at subsequent timepoints, even if the short axis decreases to < 15 mm (or even < 10 mm). However, if it subsequently decreases to < 10 mm and all other lesions are no longer detectable or have also decreased to a short axis of < 10 mm (if lymph nodes), a response assessment of complete response may be assigned.

Lymph nodes should always have the actual short axis measurement recorded (measured in the same anatomical plane as the baseline examination), even if the node regresses to < 10 mm during the study. Thus, when lymph nodes are included in the sum of diameters, the sum may not be zero even if complete response criteria are met, since a normal lymph node is defined as having a short axis of < 10 mm.

Measuring Lesions That Become Too Small to Measure

During the study, all target lesions and up to five measurable new lesions (lymph node and non-lymph node) should have their actual measurements recorded at each subsequent evaluation, even when very small (e.g., 2 mm). However, sometimes lesions or lymph nodes become so faint on CT scan that the radiologist may not feel comfortable assigning an exact measurement and may report them as being too small to measure. When this occurs, it is important that a value be recorded on the CRF, as follows:

- If it is the opinion of the radiologist that the lesion has likely disappeared, the measurement should be recorded as 0 mm.
- If the lesion is believed to be present and is faintly seen but too small to measure, a default value of 5 mm should be assigned and "too small to measure" should be

